GGT	Gamma Glutamyl Transferase
GMFR	Geometric Mean Fold Rise
GMT	Geometric Mean Titer
HCT	Hematocrit
HD	High Dose
HGB	Hemoglobin
HIPAA	Health Insurance Portability and Accountability Act
HLA	Human Leukocyte Antigen
IB	Investigator's Brochure
ICF	Informed Consent Form
ICH	International Conference on Harmonization
ICMJE	International Committee of Medical Journal Editors
IDE	Investigational Device Exemption
IEC	Independent or Institutional Ethics Committee
IM	Intramuscular
IND	Investigational New Drug Application
IRB	Institutional Review Board
ISM	Independent Safety Monitor
ITT	Intention to Treat
JAMA	Journal of the American Medical Association
JEV	Japanese Encephalitis Virus
L	Liter
LD	Low Dose
LLN	Lower Limit of Normal
MAR	Missing at Random
MCAR	Missing Completely at Random
mcg	Microgram
MD	Medium Dose
MedDRA®	Medical Dictionary for Regulatory Activities

List of Abbreviations (continued)

mEq	Milliequivalent
mg	Milligram
mITT	Modified Intention to Treat
mL	Milliliter
mmHg	Millimeters of Mercury
MNAR	Missing Not at Random
MOP	Manual of Procedure
N	Number (typically refers to subjects)
NCI	National Cancer Institute, NIH, DHHS
NDA	New Drug Application
NEJM	New England Journal of Medicine
NIAID	National Institute of Allergy and Infectious Diseases, NIH, DHHS
NIH	National Institutes of Health
OCRA	Office of Clinical Research Affairs, DMID, NIAID, NIH, DHHS
OHRP	Office for Human Research Protections
OHSR	Office for Human Subjects Research
ORA	Office of Regulatory Affairs, DMID, NIAID, NIH, DHHS
PBMCs	Peripheral Blood Mononuclear Cells
PFU	Plaque Forming Units
PHI	Protected Health Information
PI	Principal Investigator
PP	Per Protocol
PREP	Public Readiness and Emergency Preparedness
PT	Preferred Term
QA	Quality Assurance
QC	Quality Control
RBC	Red Blood Cell
RCD	Reverse Cumulative Distribution
RNA	Ribonucleic Acid
SAE	Serious Adverse Event
SD	Standard Deviation

List of Abbreviations (continued)

SDCC	Statistical and Data Coordinating Center
SMC	Safety Monitoring Committee
SOC	System Organ Class
SOP	Standard Operating Procedure
TBEV	Tick-borne Encephalitis Virus
U	Units
ULN	Upper Limit of Normal
US	United States
VTEU	Vaccine and Treatment Evaluation Unit
WBC	White Blood Cells
WHO	World Health Organization
WNV	West Nile Virus
WRAIR	Walter Reed Army Institute of Research
YFV	Yellow Fever Virus
ZIKV	Zika Virus
ZPIV	Zika Virus Purified Inactivated Vaccine

1. PREFACE

This Statistical Analysis Plan (SAP) for DMID Protocol 16-0034, “*Phase I, Randomized, Double-blinded, Placebo-Controlled Dose De-escalation Study to Evaluate the Safety and Immunogenicity of Alum Adjuvanted Zika Virus Purified Inactivated Vaccine (ZPIV) Administered by the Intramuscular Route in adult Subjects Who Reside in a Flavivirus Endemic Area*

” describes and expands upon the statistical information presented in the protocol.

This document describes all planned analyses and provides reasons and justifications for these analyses. It also includes sample tables, listings, and figures planned for the final analyses. Regarding the final analyses and Clinical Study Report (CSR), this SAP follows the International Conference on Harmonisation of Technical Requirements for Registration of Pharmaceuticals for Human Use (ICH) Guidelines, as indicated in Topic E3 (Structure and Content of Clinical Study Reports), and more generally is consistent with Topic E8 (General Considerations for Clinical Trials) and Topic E9 (Statistical Principles for Clinical Trials). The structure and content of the SAP provides sufficient detail to meet the requirements identified by the FDA and ICH, while all work planned and reported for this SAP will follow internationally accepted guidelines published by the American Statistical Association and the Royal Statistical Society for statistical practice.

This document contains four sections: (1) a review of the study design, (2) general statistical considerations, (3) comprehensive statistical analysis methods for immunogenicity and safety outcomes, and (4) shells of proposed tables and data listings and mock figures. Within the table, figure, and listing mock-ups (Appendices 1, 2, and 3), references to CSR sections are included. Any deviation from this SAP will be described and justified in protocol amendments and/or in the CSR, as appropriate. The reader of this SAP is encouraged to also review the study protocol for details on conduct of the study and the operational aspects of clinical assessments.

2. INTRODUCTION

Zika virus (ZIKV) disease (also known as Zika) is an emerging mosquito-borne disease caused by an RNA virus from the family *Flaviviridae*, genus *Flavivirus*. As a Flavivirus, ZIKV is related to the four dengue viruses (DENV 1-4), West Nile virus (WNV), Japanese encephalitis virus (JEV), yellow fever virus (YFV), and tick-borne encephalitic virus (TBEV). The majority of human ZIKV infections result in an asymptomatic infection or a benign, self-limited acute febrile illness. ZIKV infections are characterized primarily by the presence of rash, fever, conjunctivitis, and/or arthralgia, which have been found in the majority of cases seeking care or detected by public health surveillance [8]. In February 2016, the World Health Organization (WHO) declared the emerging ZIKV epidemic a “Public Health Emergency of International Concern.” Active mosquito-borne transmission of ZIKV has now been reported in more than 35 countries in South America, Central America, and the Caribbean including Puerto Rico (PAHO 2016).

There is no specific treatment or vaccine currently available to treat or prevent ZIKV infections, other than mosquito control measures. Development of a preventive vaccine against ZIKV infections is a high global public health priority. The ZIKV vaccine used in this trial is a purified inactivated virus vaccine that was produced by the Walter Reed Army Institute of Research (WRAIR). ZPIV is intended to be used in flavivirus endemic areas and among US military members and travelers who may have already received another flavivirus vaccine. Therefore, evaluating the safety and immune response in both flavivirus-naïve and flavivirus-immune subjects is important. This clinical trial was conducted in Puerto Rico, whose population has been exposed to at least the flaviviruses, DENV 1-4 and ZIKV, with potential exposure to WNV in visits to the mainland U.S. and YFV through vaccination. This study setting provides the opportunity to evaluate ZPIV among a largely flavivirus-immune population residing in an area with active ZIKV and DENV transmission.

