3. STUDY OBJECTIVES AND ENDPOINTS

3.1. Study Objectives

Primary Objectives:

1. Assess the safety and reactogenicity of a homologous prime boost regimen of ZPIV given at two different dose levels in a dose de-escalation format in healthy adult subjects who live in Puerto Rico, a flavivirus endemic area.
2. Compare the safety and reactogenicity profile of ZPIV after each vaccination, between dosage groups, and by pre-vaccination flavivirus immune status.

Secondary Objectives:

1. Assess the humoral immune response to a homologous prime-boost regimen of ZPIV after each dose of vaccine as determined by kinetics of the immune responses, seroconversion rates, and Geometric Mean Titers (GMT) overall, and compare results between dosage groups and by pre-vaccination flavivirus immune status.
2. Assess the durability of the humoral immune response to ZPIV at 6, 12, 18, and 24 months after the second vaccine administration overall, and compare results between dosage groups and by pre-vaccination flavivirus immune status.

Exploratory Objectives

1. Estimate the incidence of ZIKV and DENV infections between Visit 00 and the subject's last visit and describe the clinical presentation including disease severity overall, by dosage group, product received, and pre-vaccination flavivirus immune status.

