1. Number and proportion of subjects who develop an acute febrile illness (AFI) or an acute rash illness (ARI) who have evidence of acute ZIKV or DENV infection detected within 14 days of symptom onset. This endpoint will be analyzed for all subjects overall, and by dosage group, product received, and pre-vaccination flavivirus immune status.
2. Number and severity of laboratory confirmed ZIKV and DENV infections during the study, overall, by treatment group, and pre-vaccination immune status, where severity is described by:
 - Duration of symptoms
 - Grade of symptoms (mild, moderate, severe)
 - Use of concomitant medications
 - Need for hospitalization or other medical care

Laboratory confirmation will be made by AFI or ARI with either: 1) evidence of acute ZIKV and DENV infection within 14 days of symptom onset or 2) a 4-fold rise in DENV or ZIKV neutralization titers between samples collected at the last visit prior to and at the first visit following the AFI/ARI, where available.

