Baseline DENV and ZIKV serostatus will be determined via IgM antibody and IgG ELISA assays, with subject results reported as either 'positive' or 'negative'. If a subject has a positive ZIKV result from either the IgM or IgG ELISA assays, they will be considered ZIKV seropositive at baseline. If a subject has inconclusive results for their baseline flavivirus immune status, they will not be included in analyses stratified by baseline flavivirus immune status but will be included in analyses of all subjects.

Post-Baseline Seropositivity

Seropositivity post-baseline is defined as a titer ≥ 10 and ≥ 100 for ZIKV MN50 and a titer ≥ 200 and ≥ 600 for ZIKV ELISA.

Seroconversion

Seroconversion for ZIKV MN50 titers and ZIKV ELISA titers is defined as ≥ 4 -fold rise from baseline.

Acute Febrile Illness and Acute Rash Illness

Acute febrile illness (AFI) is defined as grade 1 or higher fever on at least 2 consecutive days accompanied by any of the following: new rash not limited to vaccination site, arthralgia, or nonpurulent conjunctivitis. Acute rash illness (ARI) is defined as any new rash not limited to vaccination site.

Laboratory Confirmation of ZIKV or DENV Infection Among Those with AFI or ARI

Among subjects with AFI or ARI, laboratory confirmation of ZIKV or DENV infection will be made by either 1) evidence of acute ZIKV and DENV infection within 14 days of symptom onset (confirmed via PCR) or 2) a 4-fold rise in DENV or ZIKV neutralization titers between samples collected at the last visit prior to and at the first visit following the AFI/ARI illness visit, where available.

Consideration of ZIKV Microneutralization Assay Results in Analysis

The lower limit of quantitation (LLOQ) for ZIKV microneutralization assay results is 10. Any values less than the LLOQ will be assigned a value of 5 by the lab. This imputed value will be used for the purpose of calculating summary statistics such GMT and will be displayed in listings of immunogenicity data. If a subject has a baseline titer below the LLOQ (reported as 5), then they will be considered seroconverted if the post-baseline titer is at least 20 (at least a 4-fold rise). Similarly, a subject with a baseline ZIKV MN50 below the LLOQ will be considered seropositive if the post-baseline titer is at least 10 or 100, as applicable.

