4.5. Immunogenicity and Safety Variables

In general, multiple observations within a specific visit period were accepted. In the case of multiple observations within a specific window, the assessment value closest to the scheduled visit date will be used in the analyses for the post-baseline records. If observations have the same distance to the scheduled assessment, the latest one will be used. Unless otherwise specified, the last assessment value recorded prior to the prime dose will be used as baseline. All the recorded data will be listed. Samples from days on which a subject was vaccinated were collected prior to vaccination.

All subjects were to have venous blood samples for assessment of humoral immunity collected on Days 1, 15, 29, 43, 57, 209, 388, and 569. Assay results are reported as the ZIKV titers giving 50% reduction in viral infection (MN50) and IgG ELISA titers. DENV neutralization titers were also to be recorded in subjects reporting ARI or AFI. Samples from the immunogenicity visits immediately before and after the illness visit were used to measure DENV titers, which will be used to aid laboratory confirmation of ZIKV/DENV infection.

Solicited adverse events were collected from the time of study vaccine administration through Day 8 after each dose. Subjects received a memory aid to record any solicited AEs on each day. The following injection site reactogenicity events were measured and grading according to the scale in [Table 3](#) and [Table 4](#): pain, tenderness, pruritis, ecchymosis, erythema, and induration. The following systemic solicited events were measured and graded according to the scale in [Table 4](#) and [Table 5](#): feverishness, fatigue, malaise, myalgia, arthralgia, headache, nausea, vomiting, diarrhea, abdominal pain, rash, and fever.

Vital signs of heart rate and blood pressure were measured in subjects at Days 1, 2, 8, 15, 29, 30, 36, 43, and 57. The measurements were assessed for adverse events of bradycardia/tachycardia and systolic and diastolic hypotension/hypertension according to the scale in [Table 6](#).

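### Exploratory Objective 1 names the incidence of ZIKV and DENV infections, but the plan counts only infections that present as AFI or ARI

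*SAP*

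**What the plan says.** The objective, in Protocol Section 3.1.3 and SAP Section 3.1, is "Estimate the incidence of ZIKV and DENV infections between Visit 00 and the subject's last visit", followed by a description of clinical presentation and severity. It is not restricted to infections with symptoms.

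The counting rules are restricted:

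- SAP Section 3.2, exploratory endpoint 2 (also Protocol Section 3.2.3): "Laboratory confirmation will be made by AFI or ARI with either" evidence of acute infection or a 4-fold neutralization rise across the illness. Endpoint 1 also starts from subjects with AFI or ARI.
- SAP Section 3.3: "Among subjects with AFI or ARI, laboratory confirmation of ZIKV or DENV infection will be made by either" PCR-based evidence within 14 days of onset or the 4-fold rise.
- SAP Section 3.3 defines AFI as "grade 1 or higher fever on at least 2 consecutive days accompanied by any of the following": a new rash beyond the vaccination site, joint pain, or nonpurulent conjunctivitis. ARI is such a rash alone.
- Protocol Section 11.4.4 and SAP Section 9.9 repeat the illness condition.
- The shells of Tables 147–153 are titled as numbers of laboratory-confirmed ZIKV or DENV infections. Percentages are taken over the Safety population, and AFI/ARI appears only in the footnotes. (SAP Section 9.9 swaps the numbers of these tables with Tables 154–158; the numbers used here follow the shells.)

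The SAP introduction states: "The majority of human ZIKV infections result in an asymptomatic infection or a benign, self-limited acute febrile illness". No section plans a search for infection in subjects who report no AFI or ARI.

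Late ZIKV titres are planned for everyone. SAP Section 3.1 has the objective "Assess the durability of the humoral immune response to ZPIV at 6, 12, 18, and 24 months after the second vaccine administration overall", and SAP Section 4.5 says: "All subjects were to have venous blood samples for assessment of humoral immunity collected on Days 1, 15, 29, 43, 57, 209, 388, and 569". Protocol Table 2 also schedules serum at Day 750. DENV neutralization titres are run only in subjects who report AFI or ARI (SAP Section 4.5).

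**The concern.** The figure that the plan produces is narrower than the one that the objective names. An infection with no symptoms, or with mild symptoms that include neither rash nor the qualifying fever, cannot enter Tables 147–153, although the subject stays in the denominator. The title and the Safety-population percentage invite the reader to take the result as the risk of infection. The exact confidence interval beside it describes sampling error only and says nothing about infections that were never looked for.

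At stake is how the clinical study report describes natural infection in an endemic setting, and whether a figure that is too low is carried into later planning. The late ZIKV titres bear on the same question, but they are summarised only as levels or as change from the pre-vaccination baseline. A rise between two late visits in a subject without illness would go unsummarised.

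**Working it through.** **The plan's own figures.** The documents give no infection risk and no symptomatic share, so there is no stated figure on this point to reproduce. The only design calculation is the chance of seeing at least one adverse event. For 80 ZPIV recipients at a true rate of 2.0%, 1 − (1 − 0.02)^80 = 80.14%, against 80.1% in SAP Table 8. It reproduces and does not bear on the question.

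**Objective against ascertainment.**

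| Step | What it covers |
|---|---|
| Objective (SAP 3.1) | All ZIKV and DENV infections, Visit 00 to last visit |
| Endpoints (SAP 3.2) and rule (SAP 3.3) | Infections in subjects with AFI or ARI, then confirmed |
| Tables 147–153 | The same restricted cases, divided by all Safety subjects |

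The counted set is a subset of the set named in the objective, so the illness condition cannot raise the estimate.

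**Illustration of size.** Let s be the fraction of infections that meet the AFI/ARI definition and are confirmed. Then

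reported incidence = true incidence × s, and the understatement factor = 1/s.

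N = 90 comes from SAP Section 4.4.3 (45 + 35 ZPIV, 5 + 5 placebo). The true risk and s are assumptions.

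| True risk | Expected infections | Counted at s = 20% / 50% / 80% | Reported |
|---|---|---|---|
| 5% | 4.5 | 0.9 / 2.25 / 3.6 | 1% / 2.5% / 4% |
| 10% | 9 | 1.8 / 4.5 / 7.2 | 2% / 5% / 8% |
| 20% | 18 | 3.6 / 9 / 14.4 | 4% / 10% / 16% |

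The factor 1/s is 5 at s = 20%, 2 at 50% and 1.25 at 80%. The Clopper-Pearson interval does not repair this. Nine of 90 gives 4.7% to 18.1%. If only 2 of those 9 are counted, 2 of 90 gives 0.3% to 7.8%, which excludes 10%.

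**What the late ZIKV titres can add.** If every scheduled visit is assayed, there are four intervals that do not span a vaccination: Days 57–209, 209–388, 388–569 and 569–750. Table 14 lists all these visits. The MN50 shells (Tables 20, 24 and 26) list only Days 57, 209 and 750 from this period, which leaves two intervals: 57–209, and 209–750 (541 days). So no new assay is needed for at least two intervals.

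A rise is easier to see from a flat titre than from a falling one. If a titre would have waned by a factor w over the interval, an infection must lift it 4w-fold above that waned level to register as a 4-fold rise. For a flat titre w = 1. For a waning vaccine response w exceeds 1, so masking may be greater in ZPIV recipients than in placebo recipients.

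**The case against.** The strongest reply is that the restriction is open. Both endpoints state it, Protocol Section 11.1 presents the activity as febrile and rash illness surveillance for preliminary data, and the other AFI/ARI tables (140–146 and 154–188) carry the illness term in their titles. This stands for a reader of the endpoints. It does not cure the wording of the objective or the titles of Tables 147–153.

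Four further points limit what may be concluded, and all but the last stand in full:

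- A reader might infer from the SAP introduction that most infections are silent and the undercount is large. The sentence says asymptomatic *or* benign febrile illness, gives no split, and concerns ZIKV only. The next sentence names rash, fever, conjunctivitis and arthralgia, which are the AFI/ARI signs. Neither document gives a silent share for DENV.
- A reader might infer that the existing titres would supply the missing incidence. They would not. They cannot recover silent DENV infection or anything before Day 57. A rise that declines again within a long interval can be missed, cross-reactive exposure may mimic a rise, and waning may mask one.
- A reader might infer that the illness trigger confuses prevention with attenuation in a vaccine comparison. With about 10 placebo recipients, descriptive surveillance and no null hypothesis under test (SAP Section 5), no such comparison is planned.
- Listing 8 already shows each subject's titres by visit, so late rises can be found by eye. That is true, but a listing applies no stated criterion and gives no count.

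**Conclusion.** The mismatch holds on the text alone. Objective 1 names infections, while the plan tabulates laboratory-confirmed infections that present as AFI or ARI. The direction follows from the definition: taking confirmed cases as true infections, the figure can only understate infection incidence, or equal it if no infection escapes the definition. The size cannot be estimated from the documents. The 1.25-fold to 5-fold range rests wholly on an assumed capture fraction of 80% to 20% and is no evidence of how large the gap is. For DENV even the presence of a gap has no stated support beyond the logic of the rule. This is a matter of labelling and completeness in an exploratory analysis, and a cheap improvement.

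**What to change.** **Relabel.** Describe the estimate for Exploratory Objective 1, the titles of Tables 147–153 and the matching text of the clinical study report as *laboratory-confirmed symptomatic (AFI/ARI) ZIKV or DENV infections*. This costs wording only and is worth doing even if the supplement is declined.

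**Supplement.** Add one descriptive table, overall and by treatment group, without between-group inference. It counts subjects with a 4-fold or greater ZIKV MN50 rise between consecutive available samples both drawn on or after Day 57, split by whether an AFI/ARI was reported. Its footnote should say that:

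- it covers ZIKV only, and only the period after Day 57;
- it uses whichever late visits were assayed (at least Days 57, 209 and 750);
- cross-reactive exposure may mimic a rise;
- waning vaccine titres may mask a rise more in ZPIV recipients than in placebo recipients.

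The table reuses planned titres and the plan's own 4-fold criterion, so the cost is programming one table.

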3. STUDY OBJECTIVES AND ENDPOINTS

3.1. Study Objectives

Primary Objectives:

1. Assess the safety and reactogenicity of a homologous prime boost regimen of ZPIV given at two different dose levels in a dose de-escalation format in healthy adult subjects who live in Puerto Rico, a flavivirus endemic area.
2. Compare the safety and reactogenicity profile of ZPIV after each vaccination, between dosage groups, and by pre-vaccination flavivirus immune status.

Secondary Objectives:

1. Assess the humoral immune response to a homologous prime-boost regimen of ZPIV after each dose of vaccine as determined by kinetics of the immune responses, seroconversion rates, and Geometric Mean Titers (GMT) overall, and compare results between dosage groups and by pre-vaccination flavivirus immune status.
2. Assess the durability of the humoral immune response to ZPIV at 6, 12, 18, and 24 months after the second vaccine administration overall, and compare results between dosage groups and by pre-vaccination flavivirus immune status.

Exploratory Objectives

1. Estimate the incidence of ZIKV and DENV infections between Visit 00 and the subject's last visit and describe the clinical presentation including disease severity overall, by dosage group, product received, and pre-vaccination flavivirus immune status.

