#### **11.4.3 Immunogenicity Analysis**

The percentage of subjects overall, by baseline flavivirus immune status, and by treatment group that seroconvert to ZIKV (as measured by ELISA and neutralization assay) will be described using exact 95% confidence intervals (CI). In addition, the geometric mean fold rise (GMFR) compared with baseline (Visit 00) will be summarized by baseline flavivirus immune status, treatment group and visit.

Subject-specific peak and per-visit results will be described. In addition, peak and per-visit GMTs and 95% CIs for each treatment group and baseline flavivirus immune status will be provided.

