3.2. Endpoints

Primary Endpoints:

1. Frequency and severity of solicited injection site and systemic reactogenicity from time of study vaccine administration through Day 8 after each administration of study vaccine overall and by dosage group and pre-vaccination flavivirus immune status.
2. Frequency and severity of unsolicited vaccine-related adverse events (AE), including vaccine-related laboratory AE, from first administration of study vaccine until 28 days after the last vaccination overall and by dosage group and pre-vaccination flavivirus immune status.
3. Frequency, type, and duration of serious adverse events (SAE) and adverse events of special interest (AESI) considered related to study vaccine from the first administration of study vaccine until the end of the study overall, and by dosage group and pre-vaccination flavivirus immune status.
4. Frequency of new onset chronic medical conditions reported at any time from the first administration of study vaccine until the end of the study overall, and by dosage group and pre-vaccination flavivirus immune status.
5. Comparison of the frequency, type and duration of vaccine-related Grade 3 local, systemic, or laboratory AE, and Grade 2 or greater local or systemic reactogenicity through Day 8 after each

study vaccine administration between dosage groups and by pre-vaccination flavivirus immune status.

6. Comparison of study withdrawals and discontinuation of study vaccination due to any reason between dosage groups and by pre-vaccination flavivirus immune status.

Secondary Endpoints:

1. Frequency of seroconversion to ZIKV at each post-vaccination visit measured by ZIKV ELISA and neutralization assay in comparison with baseline samples (collected at Visit 00) overall, and by dosage group and pre-vaccination flavivirus immune status.
2. Per Visit GMT as measured by ZIKV ELISA and neutralization assay after each study vaccine administration and for each post-vaccination visit overall, and by dosage group and pre-vaccination flavivirus immune status.
3. Peak GMT as measured by ZIKV ELISA and neutralization assay after each vaccination and overall, and by dosage group and pre-vaccination flavivirus immune status.
4. Proportion of subjects with at least a 4-fold rise in ZIKV GMT as measured by ZIKV ELISA and neutralization assay at 4 weeks after each vaccination compared with baseline overall, and by dosage group and pre-vaccination flavivirus immune status.

Exploratory Endpoints:

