8.2. Secondary Immunogenicity Analyses

8.2.1. ZIKV Microneutralization Antibodies (MN50)

Seropositivity rates will be calculated based on ZIKV MN50 titers ≥ 10 and ≥ 100 . Seroconversion rates will be calculated based on the number of subjects experiencing at least a 4-fold rise in ZIKV MN50 titers from baseline.

Geometric mean titer (GMT) and 95% CI for ZIKV MN50 results at each visit and for peak titer results will be summarized by treatment group overall and by baseline flavivirus immune status for the immunogenicity (IMM) population in [Table 20](#) and per protocol (PP) population in [Table 21](#).

Geometric mean fold rise from baseline (GMFR) and 95% CI results at each post-baseline visit and for each subject's peak ZIKV MN50 titer results will be summarized by treatment group overall and by baseline flavivirus immune status for the IMM population in [Table 22](#) and PP population in [Table 23](#).

Seropositivity rates and 95% CIs at each visit and for peak ZIKV MN50 titer results will be summarized by treatment group overall and by baseline flavivirus immune status for the IMM population in [Table 24](#) and PP population in [Table 25](#).

Seroconversion rates and 95% CI at each post-baseline visit and using peak titer results will be presented by treatment group overall and by baseline flavivirus immune status for the IMM population in [Table 26](#) and PP population in [Table 27](#). Denominators for percentages will be the number of subjects with non-missing data at the applicable time point and 95% CI will be calculated using Clopper-Pearson methodology from a binomial distribution.

Graphical presentations of immune response by treatment group and baseline flavivirus immune status will include reverse cumulative distribution curves ([Figure 2](#) through [Figure 11](#) and longitudinal presentation of GMTs ([Figure 16](#) and [Figure 17](#)), seropositivity at a threshold of ≥ 10 ([Figure 18](#) and [Figure 19](#)), seropositivity at a threshold of ≥ 100 ([Figure 20](#) and [Figure 21](#)), and percent seroconversion ([Figure 22](#) and [Figure 23](#)).

A listing of ZIKV MN50 titers by subject, treatment group, baseline flavivirus immune status, planned time point, and actual study day is presented in [Listing 8](#).

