8.2.2. ZIKV ELISA Antibodies

Seropositivity rates will be calculated based on ZIKV IgG ELISA titers ≥ 200 and ≥ 600 . Seroconversion rates will be calculated based on the number of subjects experiencing at least a 4-fold rise in ZIKV IgG ELISA titers from baseline.

The analyses described in Section [8.2.1](#) will be repeated for ZIKV ELISA titers: GMT and 95% CI results are presented in [Table 28](#) (IMM) and [Table 29](#) (PP), GMFR and 95% CI results are presented in [Table 30](#) (IMM) and [Table 31](#) (PP), seropositivity rates and 95% CIs are presented in [Table 32](#) (IMM) and [Table 33](#) (PP), and seroconversion results and 95% CIs are presented in [Table 34](#) (IMM) and [Table 35](#) (PP). Denominators for percentages will be the number of subjects with non-missing data at

the applicable time point and 95% CI will be calculated using Clopper-Pearson methodology from a binomial distribution.

Graphical presentations of immune response by treatment group and baseline flavivirus immune status will include reverse cumulative distribution curves ([Figure 24](#) through [Figure 35](#)) and longitudinal presentation of GMTs ([Figure 38](#) and [Figure 39](#)), seropositivity at a threshold of ≥ 200 ([Figure 40](#) and [Figure 41](#)), seropositivity at a threshold of ≥ 600 ([Figure 42](#) and [Figure 43](#)), and percent seroconversion ([Figure 44](#) and [Figure 45](#)).

A listing of ZIKV ELISA titers by subject, treatment group, baseline flavivirus immune status, planned time point, and actual study day is presented in [Listing 8](#).

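### The shells for Tables 20-35 have no rows for Days 15, 43, 388 and 569, which SAP 8.2 and endpoints 1-2 cover, and no analysis gives the peak GMT after each vaccination that endpoint 3 asks for.

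*SAP*

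**What the plan says.** **Objectives and endpoints (SAP 3.1 and 3.2).** Objective 1 concerns the humoral response after each dose, "as determined by kinetics of the immune responses, seroconversion rates, and Geometric Mean Titers (GMT) overall". Objective 2 names four durability times: "Assess the durability of the humoral immune response to ZPIV at 6, 12, 18, and 24 months after the second vaccine administration overall". Endpoint 1 is "Frequency of seroconversion to ZIKV at each post-vaccination visit", by ELISA and neutralization assay. Endpoint 2 is the per-visit GMT, "after each study vaccine administration and for each post-vaccination visit overall". Endpoint 3 is "Peak GMT as measured by ZIKV ELISA and neutralization assay after each vaccination and overall".

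**Methods text.** SAP 8.2.1 plans "Geometric mean titer (GMT) and 95% CI for ZIKV MN50 results at each visit and for peak titer results" and sends these to Tables 20 and 21. Fold rise, seropositivity and seroconversion follow in Tables 22-27, again at each visit and at the peak. SAP 8.2.2 says that these analyses "will be repeated for ZIKV ELISA titers: GMT and 95% CI results are presented in" the first of Tables 28-35. Protocol 11.4.3 agrees: "peak and per-visit GMTs and 95% CIs for each treatment group and baseline flavivirus immune status will be provided".

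**Shells (SAP Appendix 1).** Tables 20 and 24 have rows for baseline, Days 29, 57, 209 and 750, and *Peak Post-Baseline*. Table 26 has the same rows without baseline. Ten other tables are told to copy one of these formats. Tables 21-23 are listed under Table 20 with no shell of their own.

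**The concern.** The methods text and the shells describe different sets of visits for the same tables. If the programmer follows the shells, the report will count subjects with data at 12 and 18 months in Table 14 but tabulate no GMT, fold rise, seropositivity or seroconversion for those visits. The earlier of the two samples taken within 28 days of each dose (Day 15 after dose 1, Day 43 after dose 2) would also go untabulated, although objective 1 asks for kinetics after each dose.

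The peak is a separate matter. Endpoint 3 wants it after each vaccination. One unsplit peak does not say which dose produced it, so the endpoint is not delivered as written.

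**Working it through.** The plan states no figure to reproduce here. The check is a comparison of visit lists.

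| Study day | Timing | Serum drawn (Protocol Table 2) | SAP 4.5 | SAP Table 13 | SAP Table 14 | Row in shells 20, 24, 26 |
|---|---|---|---|---|---|---|
| 15 | after dose 1 | yes | yes | yes | yes | **no** |
| 29 | before dose 2 | yes | yes | yes | yes | yes |
| 43 | 14 days after dose 2 | yes | yes | yes | yes | **no** |
| 57 | 28 days after dose 2 | yes | yes | yes | yes | yes |
| 209 | 6 months after dose 2 | yes | yes | yes (printed as Day 290) | yes | yes |
| 388 | 12 months | yes | yes | yes | yes | **no** |
| 569 | 18 months | yes | yes | yes | yes | **no** |
| 750 | 24 months | yes | not listed | yes | yes | yes |

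**Visits.** There are 8 post-vaccination draws and 4 shell rows, so 8 − 4 = 4 visits have no row.

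**Durability times.** Objective 2 corresponds to Days 209, 388, 569 and 750. Days 388 and 569 have no row: 2 of 4.

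**Samples within 28 days of a dose.** Days 15 and 29 follow dose 1; Days 43 and 57 follow dose 2. The shells show 1 of 2 for each dose.

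**Tables affected.** Three are drawn (20, 24, 26). Ten are told to copy a format (25, 27 and 28-35). Three have no shell of their own (21-23). 3 + 10 + 3 = 16.

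**Is a reduction recorded?** SAP Section 15 lists the changes to enrollment, the interim analyses, baseline flavivirus testing and infection confirmation. None removes an immunogenicity visit. SAP Section 1 says that departures from the SAP will be described and justified.

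**Peak.** On the full set, the visits after dose 1 are Days 15 and 29, and those after dose 2 are Days 43, 57, 209, 388, 569 and 750. Neither per-dose peak has a row (0 of 2). On the shell visits alone, Day 29 is the only visit after dose 1, so its row serves as that peak. The maximum of Days 57, 209 and 750 has no row (1 of 2 delivered).

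**Why the visits behind a peak should be stated.** This illustration uses assumptions that are not in the documents: equal true mean titre at every visit and independent normal within-subject error with SD 0.15 to 0.30 log10. By simulation, the geometric mean of the maximum exceeds the true value as follows:

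- SD 0.15: 1.63-fold over 8 visits and 1.43-fold over 4; the ratio of the unrounded values is 1.15.
- SD 0.30: 2.68-fold over 8 visits and 2.04-fold over 4; ratio 1.31.

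Real titres rise and wane, so these ratios show only that the visit set can move a peak GMT. They do not predict the size of the effect in this trial.

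**The case against.** **The shells are only proposals.** SAP Section 1 calls them that, and 8.2 already asks for every visit, so a programmer who follows the text would add the rows. That limits the harm but does not remove the contradiction, since the shells list specific rows.

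**The restriction may be deliberate.** The same visit list appears in three separately drawn shells, which fits a decision about which samples to assay as well as it fits an oversight. No passage says which samples were assayed. This stands: a reader might infer that the shells are simply wrong, and the documents do not establish that. If the shells are right, then objective 2, endpoints 1-2, SAP 8.2 and Tables 13-14 need the correction.

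**The results may appear elsewhere.** Listing 8 gives each titre by planned time point. SAP 8.2 also plans longitudinal figures of GMT, seropositivity and seroconversion. The figures cannot be seen, so nothing can be said about which visits they show. A reader might infer that 12- and 18-month results will be lost from the report; the documents support only their absence from the summary tables.

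**The protocol also leaves the peak unsplit.** Its analysis text in 11.3.1 and 11.4.3 mentions the peak without dividing it by dose, so the SAP did not cut back a split that the protocol's analysis section had specified. The gap lies between endpoint 3 and the analysis text of both documents. The row label most naturally means all post-baseline visits; it becomes uncertain only because the shells show half of them. In endpoint 3, overall may also mean all subjects pooled, so the firm shortfall is the peak after each vaccination.

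**The outcomes are descriptive and secondary** in a study that Protocol 11.1 describes as exploratory. That is fair, and it bears on priority.

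**Conclusion.** The point holds as an internal contradiction that should be resolved before the tables are programmed. As drawn, the shells leave 4 of 8 post-vaccination visits and 2 of 4 named durability times without a row across the 16 tables, taking Tables 21-23 to follow Table 20. No analysis delivers endpoint 3's peak GMT after each vaccination.

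Two limits apply. Objective 2 might be read as requiring all four missing days, but it names only the 6-, 12-, 18- and 24-month times and so covers Days 388 and 569. Days 15 and 43 follow from endpoints 1-2, SAP 8.2, SAP 4.5 and Tables 13-14. Endpoint 4 (the 4-fold rise at 4 weeks after each dose) is unaffected, because Days 29 and 57 have rows.

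A reader might also infer that late peaks are contaminated by natural infection, since the SAP describes active transmission in the area. The documents give no way to know how often that would happen, and it is not part of this finding.

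**What to change.** 1. Add rows for Days 15, 43, 388 and 569 to Tables 20-35. If those samples were not assayed, say so in SAP 8.2 and Section 15, and restate objective 2, endpoints 1-2 and Tables 13-14 to match.
2. In the GMT tables (20, 21, 28 and 29), report peak GMT after dose 1 (Day 15 and the pre-dose-2 Day 29 sample), after dose 2 (Day 43 onward) and overall, and state the visits that each uses. If Day 15 was not assayed, say that the post-dose-1 peak is the Day 29 titre.

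**Cost.** With seven strata (all subjects plus six serostatus groups), the GMT, fold-rise and seroconversion tables gain 12 × 4 × 7 = 336 rows. The seropositivity tables, with two thresholds, gain 4 × 4 × 7 × 2 = 224. That totals 560 rows, all repeats of existing blocks. The two added peaks need 2 × 7 × 4 = 56 rows and one derivation rule. No samples are needed beyond those scheduled. If the four visits were not assayed, the 560 rows are replaced by a few sentences. The downside is longer tables.

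Labelling peaks that include visits after Day 57 as possibly reflecting later infection is optional. Adding Day 750 to SAP 4.5 and changing Day 290 to Day 209 for Visit 14 in Table 13 are clerical corrections.
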